#### ***Medication use Steroids (OCS)***

Diary card: Date

Diary card: Medication (where medication includes Prednisolone and its variations)

Diary card: Dose

Diary card: Units

Diary card: Days

Diary card: Doses per day

Phone call data: Other medications used (where medication includes Prednisolone and its variations)

### ***Medication use Steroids (ICS)***

Diary card: Date

Diary card: Medication

Diary card: Dose

Diary card: Units

Diary card: Days

Diary card: Doses per day

Phone call data: Other medications used

### ***Medication use Salbutamol***

Diary card: Date

Diary card: blue inhaler used today?

Diary card: How many times blue inhaler used?

Diary card: How many puffs when blue inhaler used?

Phone call data: Other medications used (where medication includes salbutamol and its variations)

### ***Medication use IMP***

Diary card: Date

Diary card: Wheeze in last 24 hours (Yes/No)

Diary card: Cold in last 24 hours (Yes/No)

Diary card: Trial medicine used today (Yes/No)

Phone call data: Number of IMP initiations

Phone call data: Total days used

### ***Adverse events and serious adverse events***

Clinical AE term (categorised as; minor injury, GI, URTI, CNS, minor infection, allergy, cutaneous, respiratory, haem)

SAE term

SAE expected (Yes/No)

Start date

End date

Date of death

Duration in hours

Intensity (Mild, Moderate, Severe)

Action taken (none, interrupted, discontinued, reduced)

Related to study drug (Definitely not, probably not, possibly, probably, definitely)

SAE resolved (resolved, resolved with sequelae)

Sequelae details

Outcome (improved, persisting, worsened, fatal, unknown)

### ***Withdrawals***

Withdrawal (from treatment or trial)

Date of withdrawal

Reason for withdrawal (eligibility no longer met, death of participant, other adverse event, deterioration of pre-existing condition, Poor adherence to treatment, Perceived lack of efficacy, unable to locate participant, other)

Withdrawal decision by (CI, PI, Referring investigator, Carer, Participant, other)

Permission to use data (do not use any data, use partial data up to withdrawal, use all data up to withdrawal, collect and use all follow up data)

Code broken (Yes/No)

### **Timing of data collection**

Each child (participant) was followed up for 12 months post randomisation with data collection taking place at 2, 4, 6, 8, 10 and 12 months.

### **GENERAL ISSUES FOR STATISTICAL ANALYSIS**

All analyses will be conducted two sided and significance interpreted at the 5% significance level.

### **Blinding of the statistical analysis**

The statistical analysis will be conducted unblinded so that the appropriate treatment code can be used in the models fitted.

### **Analysis populations**

#### **Intent-to-treat population**

The intention-to-treat (ITT) sample is defined for this trial as all participants randomized into the trial included in the intervention group to which they were randomised.

#### **Available-case population**

The available Case (AC) sample is defined for this trial as all participants randomized into the trial included in the intervention group to which they were randomised where outcome data are available.

#### **Per protocol population**

The Per Protocol (PP) sample is defined as the available case sample with those participants who discontinue IMP or were randomised incorrectly being excluded.

#### **Safety population**

The safety population includes all participants.

#### **Other populations**

Two populations are described for the sensitivity analyses described in section 8.5. The first is based on the ITT population replacing any stratification factors that were incorrectly defined at randomisation with the corrected values. The second is based on the ITT population with the exclusion of 11 incorrectly randomised participants.

### **Database**

#### **Description**

The data were entered into and stored in a Microsoft Access database. Data were entered by trial staff who were blind to treatment group.

#### **Data quality**

Source data verification is performed for 10% of CRFs by the trial team.

#### **Database freeze and lock**

Once the trial team have completed all data entry and checking. The statistician responsible for the analysis will conduct or oversee additional data checks. These include things such as range checks, logical and consistency checks which may not be picked up by checks performed at the individual level. Procedures implemented to database lock will be followed in accordance with the relevant SOP (PCTU\_DM\_04 Standard Operating Procedures (SOP) for: Data Entry, Quality Control, Data Extraction and Database lock)

Analysis will take place when the database is considered final.

### **Analysis software**

The analysis will be carried out using Stata version 12.0.

### **Methods for withdrawals, loss to follow-up and missing data**

Those participants who withdraw and provide permission to use their data will be included in the analysis up to the point of withdrawal.

For the primary outcome phonecall data, at the time of writing (prior to unblinding) we have:

Full 12 months data on 1134/1347(84%)

29/1347 (2%) participants withdrew before the first 2 month phonecall and have no data collected as expected

12/1347 (0.9%) do not have any follow up data and this is being queried with the sites

Partial follow up data is available for 172 (13%). 44 of these participants did not formally withdraw from follow up. This is being queried with the sites

After data cleaning we expect the levels of missing data to improve. Due to these relatively low levels of missing data, and that the follow up time for each participant is to be included in the analysis no imputation of the missing data will be performed

### **Method for handling centre effects**

We do not anticipate there to be any affect of centre and this will not be adjusted for in the analysis

### **Method for handling randomisation stratification or minimisation factors**

The randomisation was stratified by genotype and this will be included as a covariate in all analyses.

### **Method for handling clustering effects**

Some outcomes are collected at the level of episode, (duration of wheeze episode, duration of cold episode, duration of hospital admission) therefore we have episode data within children. In these cases a random effect is included for child.

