## **STUDY METHODS**

### **Overall study design and plan**

Target for randomisation: 650 intervention and 650 control participants

Date of first randomisation: 25/10/2010

Date of last randomisation: 27/12/2012

Trial design: Individually randomized, parallel group

Blinding: Participants and their treating clinician are blind to treatment allocation

Randomised Interventions: Montelukast vs. placebo

Allocation ratio: 1:1

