### **Sample size determination**

This trial is powered to detect a clinically significant difference in the number of attacks of wheeze between intervention and control arms. We also had power to detect large differences responsiveness (in terms of the primary outcome) to montelukast in the stratum with ALOX5 promoter polymorphism [5/5], compared with the stratum with the ALOX5 [5/x and x/x]" genotype.

Data on mean (0.76) and standard deviation (1.22) of number of attacks come from data from the UK General Practitioner Research Database on courses of oral steroids (a proxy for number of episodes). These data follow an overdispersed Poisson distribution. To take account of this we used markov chain Monte Carlo simulation in WinBUGS to estimate sample sizes required: (WinBUGS Version 1.4. 2003 Available from: <http://www.mrc-bsu.cam.ac.uk/bugs/welcome.shtml>). To detect

a 33% drop in attack rate requiring medical attention, with a power of 90% and at a significance level of 5%, and a 6% loss to follow up, we require 1050 children in total. A 33% drop in attack rates equates to an attack rate of 0.51 for the treatment group. The clinical significance of these changes is that approximately four children will need to be treated to prevent one clinically severe attack. A sample size of 1200 gives just over 80% power at the 5% significance level to detect an interaction between treatment and genotype if the effect is a 60% reduction in the [5/x plus x/x] and a 20% reduction in the [5/5] stratum. Assuming a 6% dropout, 1300 children will need to be recruited.

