**Table 6: Medication usage**

ITT population	Montelukast N=	Placebo N=	IRR or OR (95% CI)	p-value
Steroids (OCS)				
 Number of courses, mean (SD)				
 Proportion receiving OCS, N (%)				
Steroids (ICS)				
 Proportion starting, N (%)				
Salbutamol				
 Number of puffs used per episode, mean(SD)				
Total puffs used per year				
Investigational Medicinal Product				
 Number of initiations, mean (SD)				
 Number of sachets per episode, mean (SD)				
Number of sachets used per year				

Data are analysed using Poisson regression with fixed effects for stratification factor and treatment group and a random effect for individual to account for overdispersion with follow up time fitted as the exposure.

Data are analysed using logistic regression with fixed effects for stratification factor and treatment group

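### Episode-level outcomes: the Poisson model with an unspecified child random effect can give standard errors that are somewhat too small if the effect is gamma and the data are skewed

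*SAP*

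**What the plan says.** Method for handling clustering effects lists three episode-level outcomes: the durations of wheeze episodes, cold episodes and hospital admissions. For these, "In these cases a random effect is included for child".

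The appendix tables give the model. Table 4 uses a Poisson regression with an individual random effect, and a separate sentence of its footnote applies this to the length of each hospital admission. Table 6 includes the row "Number of puffs used per episode, mean(SD") and a similar row for sachets. Both carry footnote 1: Poisson regression with a "random effect for individual to account for overdispersion with follow up time fitted as the exposure".

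The SAP does not say whether the random effect is gamma or normal. It names no robust standard error, bootstrap or episode-level dispersion term.

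There is a fallback. The assumption checks for the primary analysis comprise a likelihood ratio test against a model without the random effect and plots of residuals against fitted values. A negative binomial or another distribution is to be considered if the fit calls for it. The Secondary analysis section refers to the same checks.

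**The concern.** The primary outcome has one count per child, so the random effect is the only source of variation beyond Poisson and no assumption is made about episodes within a child. With several rows per child, the same model also assumes that one child's episodes vary as Poisson around that child's mean. At an assumed mean of 30 puffs this implies a within-child SD of √30 ≈ 5.5. The Data collection section records salbutamol as times used and puffs each time, so an episode total is a sum of multi-puff doses over days. Variation greater than Poisson is plausible, although the SAP gives no data on it.

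If the variance is wrongly shaped, model-based intervals can be too narrow and p-values too small for salbutamol and sachets per episode and, to a lesser degree, for durations. All tests are at 5% two-sided with no multiplicity adjustment, so nothing else in the plan would offset this.

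**Working it through.** **What the SAP supplies.** Two-sided 5% tests (General issues for statistical analysis), 1:1 allocation (Overall study design and plan), and 12 months of follow-up (Timing of data collection). The only dispersion figure is child-level: mean 0.76 and SD 1.22 attacks (Sample size determination). It roughly reproduces the stated total of 1050 for the main effect: 2 × (1.960 + 1.282)² × 1.22² / 0.25² ≈ 501 per arm, and 1002 / 0.94 ≈ 1066. It says nothing about variation between one child's episodes.

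**Assumed, not in the SAP.** Mean puffs or days per episode, episodes per child, and the amount and shape of within-child and between-child variation.

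**Step 1: why most of the excess is absorbed.** Let child i have m episodes, episode mean μ, a child effect with mean 1 and variance σ², and episode effects with mean 1 and variance a. For the child's total T,

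Var(T) = mμ + (mμ)² × [σ² + (1 + σ²)a/m].

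Treatment and genotype are constant within child. With a gamma effect, the episode-level likelihood for the regression terms and random-effect variance therefore equals, up to a constant, a negative binomial likelihood for T with variance mμ + α(mμ)². A numerical check gave the same difference, −326.511, at three parameter values. So α can take up the term in square brackets.

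**Step 2: what is left over.** Take m = 4, μ = 40, σ² = 0.3, a = 0.5.
- α needed: 0.3 + 1.3 × 0.5/4 = 0.4625. Average α fitted by maximum likelihood: 0.416, because the combined variation is not gamma-shaped.
- SE = √[(4/1000) × (1/(mμ) + α)] for 1000 children. Needed: √[0.004 × (0.00625 + 0.4625)] = 0.0433. Fitted: √[0.004 × (0.00625 + 0.416)] = 0.0411.
- Ratio 0.0411/0.0433 = 0.949, so type I error ≈ 2Φ(−1.96 × 0.949) = 6.3%. Simulated: 6.2%.

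If the number of episodes varies, a single α cannot match a term in 1/m. In the same setting with overdispersed episode numbers (mean 4), the model SE is 0.0478 against an empirical SD of 0.0521, and coverage is 91.3%.

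**Step 3: skew between children is enough by itself.** Suppose there is no within-child excess, child means are lognormal with CV 1 and counts are large. A gamma fit solves ln k − ψ(k) = ½ ln 2, so k = 1.589 and α = 1/k = 0.629, against a true value of 1. The SE ratio is √0.629 = 0.793, and type I error is 2Φ(−1.96 × 0.793) = 12.0%. Simulation of lognormal between-child variation alone gave 11.9%.

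**Step 4: simulated type I error under no effect (nominal 5%).**

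| Setting (assumed) | Gamma child effect, model SE | Child-robust SE |
|---|---|---|
| No within-child excess, gamma between children | 4.2% | 4.2% |
| Mean 30 puffs, gamma between children, CV 0.5–1 | 7.6–10.6% | 4.7–5.7% |
| Mean 30 puffs, lognormal at both levels | 16.6% | see below |
| Mean 5 days | 5.7–5.9% | see below |

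A second set of runs (1000 children, 1 + Poisson(2) episodes, 600 replicates) gave, for mean 30 and within-child CV 1, 7.7–8.7% with gamma and 9.2–11.3% with lognormal within-child variation. Robust errors gave 4.3–5.5%. For mean 5 days and CV 0.7 it gave 6.5–6.7% (gamma) and 8.5% (lognormal), with 4.7–5.7% for robust errors. In another set that included the most skewed scenario, robust errors gave 3.5–5.7% throughout.

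**Step 5: gamma against normal child effect.** Mean 6 per episode, between-child variance 0.3, episode numbers overdispersed with mean 4, 300 replicates:

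| Variation | Within-child variance | Gamma: coverage (SE ratio) | Normal: coverage (SE ratio) |
|---|---|---|---|
| Gamma | 0.5 | 94.7% (0.972) | 96.0% (1.039) |
| Lognormal, both levels | 0.5 | 92.0% (0.848) | 94.7% (0.950) |
| Lognormal, both levels | 1.5 | 87.3% (0.794) | 95.7% (1.040) |

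At mean 30, a normal effect gave about 4–7% type I error in 150 replicates.

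Monte Carlo error at 5% is √(0.05 × 0.95/600) ≈ 0.9 points for 600 replicates, 1.3 for 300 and 1.8 for 150.

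**The case against.** **The plan has its own remedy.** The checks allow a negative binomial or other distribution, and the secondary outcomes are referred to them. This stands in part: it would be wrong to infer that the plan commits to Poisson whatever the data show. But alternatives are only to be considered. The likelihood ratio test asks whether a child effect is needed, not whether episodes within a child exceed Poisson, and the residual plots do not target that either.

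**Puffs and sachets may not be episode-level rows.** The clustering section lists durations only. The sachet outcome is worded as a mean per episode, which could be one value per child, and salbutamol is missing from the list of outcomes for which the primary model is repeated. This stands as a condition. Table 6 assigns the model to both outcomes without saying what a row is.

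**The random effect does the job.** A reader might infer that it leaves all variation between a child's episodes unmodelled. Step 1 shows otherwise: most is absorbed, and with a normal effect intervals were close to nominal. This stands, but the plan does not say which effect will be used, so validity rests on an unstated choice.

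**The inputs are assumed.** Correct. The SAP does not establish that puffs or days are overdispersed or skewed within a child.

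**Conclusion.** The point holds in a limited form. For outcomes analysed with one row per episode, the model assumes Poisson variation within a child and leaves the random-effect distribution open. With a gamma effect and skewed variation, between or within children, model-based standard errors can be too small. Under the assumed inputs (mean 30 puffs, CV 0.5 to 1) type I error is about 8 to 11%. The figure of about 17% needs lognormal variation at both levels and is an upper scenario, not a typical value. For durations averaging 5 days it is about 6%, which is minor; it is larger only if durations are assumed strongly skewed (8.5% with lognormal CV 0.7, and 12.7% in the most extreme mean-6 setting of Step 5). With a normal effect it is near nominal.

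Not all of this comes from within-child variation: skew between children produces a similar excess without it. A reader might also infer that the primary result is affected. The primary outcome has one count per child, so the within-child assumption does not arise, and none of the figures above were computed for it. The point is a low-priority improvement to secondary analyses.

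**What to change.** In Method for handling clustering effects and in the footnotes to Tables 4 and 6:

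- State whether the child random effect is gamma or normal.
- State whether puffs and sachets per episode are analysed with one row per episode or one value per child.
- For every outcome with one row per episode, keep the log-link model and report standard errors that are robust to clustering by child, or a child-level bootstrap.

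This takes a few sentences and one change to the model command. The cost is slightly wider intervals on some secondary outcomes. Where there was no within-child excess, robust and model-based errors performed alike (4.2% each), so little is lost if the assumed skew does not occur.

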### **Method for selecting other variables that will be adjusted for**

All analysis will only be adjusted for genotype (see section 2.7).

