### **Outcome measures**

#### **Primary outcomes**

The number of times a child attends for an unscheduled medical opinion (a summation of hospital admissions, attendances, GP visits,) with respiratory problems over a 12 month period as confirmed from clinical records

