#### ***Pre-study illness and therapy (Yes/No)***

Episodic wheeze; multitrigger wheeze; admitted to hospital in last year; ever admitted to hospital; Preventer therapy none; Preventer therapy antileukotriene; Preventer therapy Maintenance inhaled steroids; Preventer therapy episodic inhaled steroids

Age at first wheeze in months

Interval between onset of URTI and wheezing (hours)

Number of courses of systemic steroids in the last year

Number of unscheduled medical attendances for wheeze in last year

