### **Primary analysis**

The primary analysis will be a Poisson regression model with the follow up time of each individual fitted as an exposure variable and with a random effect for individual to account for overdispersion.

The incident rate ratio (IRR) for the treatment effect and corresponding 95% confidence interval will be presented. An IRR of less than 1 indicates a benefit of Montelukast in reducing the rate of unscheduled medical attendance needed.

Assumption checks and actions to be taken if assumptions do not hold

The fit of the model will be compared to a model without a random effect using the likelihood ratio test, and the fit will be assessed using diagnostic plots (residuals versus fitted values), alternative distributions to the Poisson such as the Negative binomial or removal of the random effect shall be considered where necessary for improved fit.

Other analysis supporting the primary (inc. sensitivity analyses)

The primary analysis will be performed on the per-protocol population and using a CACE analysis.

It will be repeated replacing any stratification factors that were incorrectly defined at randomisation with the corrected values (see section 1.4).

It will be repeated with exclusion of 11 incorrectly randomised participants (see section 1.4).

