**Table 1: Baseline comparability of treatment groups**

ITT population	Montelukast			Placebo		
	5/5	5/x and x/x	Total	5/5	5/x and x/x	Total
Height (cm)						
Weight (Kg)						
Age (years)						
Gender						
	Male					
	Female					
Stratum						
	A					
	B					
Ethnicity						
	Asian or Asian British					
	Mixed					
	Black or Black British					
	White					
	Other					
Pre existing conditions						
	X					
	Y					
	Z					
Age at first wheeze (months)						
Interval between onset of URTI and wheezing (hours)						
Episodic wheeze						
Multi-trigger wheeze						
Admitted to hospital in last year						
Admitted to hospital ever						
Preventer therapy						
	None					
	Antileukotriene					
	Maintenance inhaled steroids					
	Episodic inhaled steroids					
Risk factors						
	Preterm birth <37 wk gestation					
	Birth weight <2500g					
	Food allergy					
	Drug allergy					
	Itchy rash for > 6 months					
	Eczema					
	Tobacco exposure in utero					
	Tobacco exposure in					

---

household  
 Daycare attendance  
 Immunised for  
 Pneumococcus  
 Immunised for influenza  
 History of asthma in  
 mother  
 History of asthma in  
 father

Numbers are N(%) or mean (SD)

This table is to be repeated for the alternative stratification (5/5 and 5/x) versus (x/x).

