**Table 3 Primary analysis: unscheduled medical attendances for wheeze over 12 months**

ITT population	Montelukast N=	Placebo N=	Adjusted IRR (95% CI) 	p-value
Follow up time (days)				
Number of :				
Any medical attendance				
All				
Stratum A				
Stratum B				
Stratum 5/5 and 5/x				
Stratum D x/x				

ICS at baseline  
Multitrigger vs episodic wheeze

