**Hospital admissions**  
**Hospital attendances (A&E or admission)**  
**Unscheduled GP visits**

**Parents considered medication to be efficacious, N(%)**

---

Data are mean (SD)

 Data are analysed using Poisson regression with fixed effects for stratification factor and treatment group a random effect for individual to account for overdispersion with follow up time fitted as the exposure. An interaction term has been included to assess whether there is a differential treatment effect dependent on stratum.

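### Adjusting only for genotype leaves out a collected near match to the primary outcome, the prior-year attendance count, and gives up a modest amount of precision, mainly on the genotype interaction

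*SAP*

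**What the plan says.** The adjustment rule is explicit and applied consistently.

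- Method for selecting other variables that will be adjusted for: "All analysis will only be adjusted for genotype (see section 2.7".
- Method for handling randomisation stratification or minimisation factors: "The randomisation was stratified by genotype and this will be included as a covariate in all analyses".
- Primary analysis: a Poisson model with follow-up time as exposure, "with a random effect for individual to account for overdispersion". The footnote to Table 3 describes "Poisson regression with fixed effects for stratification factor and treatment group" and names no other covariate.
- Subgroup analyses, Method of analysis: the primary analysis is repeated with a treatment-by-stratum interaction, so it inherits the same restriction.

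The baseline data, under Pre-study illness and therapy, include "Number of unscheduled medical attendances for wheeze in last year" and the number of systemic steroid courses in the same period. Neither appears in any primary, secondary, subgroup or sensitivity model. Neither has a row in Table 1 ("Baseline comparability of treatment groups"), which the SAP names as the source of the variables for baseline comparison. The SAP gives no reason for leaving them out.

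The primary outcome is "The number of times a child attends for an unscheduled medical opinion", for respiratory problems and confirmed from clinical records. The primary objective and the title of Table 3 ("Primary analysis: unscheduled medical attendances for wheeze over 12 months") speak of wheeze.

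**The concern.** A pre-randomisation count of nearly the same event is a natural covariate for a count outcome. The planned model leaves all stable differences between children in the random effect, where they widen the interval for the rate ratio. Part of that variation could be explained at almost no cost, because the data are already collected.

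What is at stake is precision. The interaction between treatment and ALOX5 stratum is where it counts: the SAP claims little more than 80% power for it, and only under a large contrast (a 60% against a 20% reduction). There is also a reporting gap. A chance imbalance in prior GP or A&E attendance counts, or in prior steroid courses, would not be visible in Table 1.

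**Working it through.** **Inputs.** From Sample size determination: control mean 0.76, SD 1.22, treated rate 0.51, 90% power, 5% significance, 6% loss, total 1050; interaction at N = 1200 with little more than 80% power. Two-sided testing is from the general issues section. The mean and SD describe oral steroid courses in a GP database, used there as a proxy for episodes.

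**1. The plan's own figure.** Comparing means with z = 1.960 + 1.282 = 3.242:

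n per arm = 2 × 3.242² × 1.22² / 0.25² ≈ 501, so 1002 in total, and 1002 / 0.94 = 1066.

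This is within 2% of 1050. The stated size therefore reproduces with no covariate and is not wrong. By the same formula, power is 89.6% at 987 evaluable children (1050 less 6%) and 94.8% at 1222 (1300 less 6%).

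**2. How much variance a covariate can reach.**

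- Overdispersion: k = (1.22² − 0.76) / 0.76² = 0.728 / 0.578 = 1.261.
- Var(log IRR) is proportional to 1/0.76 + 1/0.51 + 2k = 1.316 + 1.961 + 2.522 = 5.799.
- The between-child part is 2.522 / 5.799 = 43%. Only this part can be reduced.

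If baseline history explains a share R² of it, the variance falls by 0.435 × R²:

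| R² | Fall in variance | SE multiplied by | Equivalent extra children |
|---|---|---|---|
| 10% | 4.3% | 0.978 | 5% |
| 20% | 8.7% | 0.956 | 10% |
| 30% | 13.0% | 0.932 | 15% |
| 49% | 21.3% | 0.887 | 27% |

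The last row is a ceiling. If each child's rate were the same in both years, one prior-year count would give R² = kμ / (1 + kμ) = 0.958 / 1.958 = 49%.

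**3. Simulation of the count model.** Negative binomial data with the mean and k above, fitted with and without log(1 + prior-year count), 400 runs per scenario; 987 children for the main effect and 1200 for the interaction. The correlation is not in the SAP, so three values were tried. The share of 5/5 children is not given either and was set at 60%.

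| Correlation of the two counts (main-effect runs) | SE ratio, main effect | SE ratio, interaction |
|---|---|---|
| 0.14 | 0.991 | 0.993 |
| 0.27 | 0.966 | 0.971 |
| 0.46 | 0.898 | 0.912 |

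In variance, the main-effect range is 1 − 0.991² ≈ 2% to 1 − 0.898² ≈ 19%, close to the 21% ceiling of step 2. The estimate does not move: in the highest-correlation scenario the mean log IRR is −0.399 unadjusted and −0.402 adjusted.

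**4. What this means for the interaction.** Starting from 80% power, z = 1.960 + 0.842 = 2.802. Dividing by each interaction SE ratio and subtracting 1.960 gives 0.862, 0.927 and 1.111, that is, power of about 81%, 82% and 87%.

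**The case against.** The strongest reply is that nothing here is wrong. Genotype is the only stratification factor, its use is pre-specified and consistent, and a sparse covariate set is a legitimate choice. That stands: a reader might infer bias or an invalid primary test, and the SAP supports neither.

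The size is also open to challenge, and much of that challenge stands.

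- A reader might take the 49% row as the expected gain. It needs a fully stable rate and rests on steroid courses, not attendances.
- Entry requires at least two attacks and one within three months, which selects on recent history. Children enter from 10 months of age, so the youngest lack a full prior year. Both would pull the correlation down, and the low simulated case is worth only about 1% in SE.
- A reader might call the count the baseline value of the primary outcome. It is restricted to wheeze and its source is not stated, whereas the outcome definition refers to respiratory problems confirmed from records. It is a near match, not a proven identity. Nor does the SAP show that it is the strongest predictor.
- The main effect has little need of help. The missing-data section reports 1134 children with full and 172 with partial follow-up, 1306 contributing in all, against about 987 needed.
- Table 1 is not blind to severity: it shows age, hospital admission in the last year and ever, wheeze type and preventer therapy.

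Finally, the rate ratio keeps its meaning under adjustment in a log-link count model, but hazard and odds ratios do not. This limits where the change should be made.

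None of this explains why a closely related count, already collected, should go unused in the count models.

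**Conclusion.** The point holds as a missed efficiency gain, worth acting on but not essential. Adding the prior-year count would lower the SE of the log rate ratio by roughly 1% to 10%, or about 2% to 21% in variance when the analytic ceiling is included. The direction is secure, since the covariate is measured before treatment and relates to nearly the same event. The size is uncertain, because it rests on an unreported correlation, on proxy figures for the mean and SD, and at the top end on year-to-year stability that the entry criteria make unlikely.

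The benefit falls mainly on the genotype interaction, where power might rise from 80% to between 81% and 87%. It does not follow that the primary comparison is underpowered or that the sample size should change. The missing Table 1 rows are a minor reporting gap.

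**What to change.** Before unblinding, amend the section on other variables to be adjusted for, the Primary analysis section and the matching table footnotes as follows.

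1. In the primary, interaction and secondary count models, add log(1 + prior-year unscheduled attendances for wheeze) and age as fixed covariates beside genotype. Age partly allows for infants without a full prior year.
2. Leave the Cox and logistic models adjusted for genotype only, as planned.
3. Report the genotype-only primary model as a sensitivity analysis.
4. State a simple rule for missing baseline values, for example mean imputation with a missing indicator, so that no randomised child is dropped because of a covariate.
5. Add prior-year unscheduled attendances and prior-year steroid courses to Table 1.

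The cost is SAP wording, one or two extra model terms and the missing-baseline rule. No new data are needed.
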